9.3. Demographics and Other Baseline Characteristics

Descriptive summaries of the demographic and other baseline characteristics will be completed for the populations specified below, overall and by treatment group and stratum as applicable; these include:

- Demographics (Age, Gender, Race/Ethnicity, Height, Weight, BMI (calculated))
(SAF, FAS, PP1, PP2)

- Medical History (SAF)

Medical history will be coded with the Medical Dictionary for Regulatory Activities (MedDRA, according to the version specified in the Data Management Plan). Incidences of findings in medical history will be summarized by MedDRA system organ class (SOC) and preferred term (PT)

- Prior and Concomitant Medications (SAF)

Medications will be coded using the WHO Drug Dictionary (according to the version specified in the Data Management Plan). Incidences of prior and concomitant medications will be summarized by ATC level 2 and ATC level 4

- Baseline Physical Examination, including vital signs (SAF)
- Baseline ECG

9.4. Measurement of Treatment Compliance

The following parameters will be listed and summarized per subject and/or per infusion cycle:

- Body weight
- Actual dose (total and per kg body weight, based on the latest available weight measurement)
- Total dose administered
- Total number of infusions administered
- Total volume of solution administered
- Number of infusions
- Infusion times
- Use of premedication
- Overall amount of product administered (only included in data listings)

Deviations from the planned treatment schedule will be summarized by counting the number of infusion cycles that deviate from the scheduled intervals by more than the allowed intervals, and by listing all cases with more than two days deviation individually.

10. Efficacy Analysis

10.1. Primary Endpoint

The primary endpoint measure 'response' will be assessed at Week 16 on bases of the TIS score detailed in section 3.2.1: a subject is defined as responder if

- (i) the subject has a TIS score of ≥ 20 points at Week 16 and
- (ii) the subject has not met "Confirmed Deterioration" criteria at 2 consecutive visits as defined in Section 8.4 up to (including) Week 16

Otherwise the subject will be counted as a non-responder in the treatment group he was randomized to Thus subjects who discontinued from the study prior to Week 16 will also be considered as non-responders.

The proportion of responders within both treatment groups will be compared by Cochran-Mantel-Haenszel test, stratified by global disease activity (randomization stratum), using two-sided alpha level of 0.05. The primary analysis will be considered as success if the proportion of responders is significantly higher in the Octagam group compared to the placebo group.

Moreover, an exact two-sided 95% confidence-interval will be constructed for the overall difference in the proportion of responders between Octagam and placebo group, using the 'exact riskdiff' option of the SAS FREQ procedure.

In a sensitivity analysis for the primary endpoint, a logistic regression model will be applied, including global disease activity and further baseline variables as applicable as covariates.

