4.3. Randomization, Stratification and Blinding

All subjects qualified to participate in the study at Visit 2 will be randomized to one of the two treatment arms – Octagam 10% or Placebo – in a ratio of 1:1. The randomization scheme will be stratified according to the seriousness of disease before enrollment: Mild | Moderate | Severe.

The Physician's Global Disease Activity assessment will determine the correct stratum for each subject as follows: GDA value of 0-3 [mild], 4-6 [moderate], 7-10 [major]

Within the strata, the same fixed block size will be used for a balanced randomization.

This design will ensure the desired overall randomization ratio and avoid random differences between the treatment groups with respect to the seriousness of DM prior to enrollment.

The randomization scheme will only be available to the statisticians responsible for creating it, and the programmer implementing the scheme into the IRT system. No information on treatment assignment will be communicated to the sponsor or any CRO personnel responsible for the conduct of the study or the analysis of data, with the following exceptions:

- The result of randomization, i.e. the treatment group assignment of individual subjects will be reported to the hospital pharmacist or designee by a dedicated email that no other trial personnel will have access to.
- Subjects with confirmed deterioration who were crossed-over during the First Period and subjects with confirmed deterioration at Week 16 will be unblinded at Week 16 as their further continuation in the Extension Period depends on their initial assignment as described in section 4.1 above. In the analysis of the primary endpoint these subjects will be considered as non-responders in the group they were randomized to.
- In case of medical emergencies as described in the protocol (section 5.6)

Only after completion of all procedures related to data cleaning, the medical review of the data, the finalization of the statistical analysis plan, the agreement on the final subject disposition, and the formal database lock the blind will be broken and the individual treatment assignment will be added to the clinical database for analysis

5. Sequence of Planned Analyses

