A stratified analysis using Cochran-Mantel-Haenszel test will finally be applied as primary analysis, to account for the stratification of the randomization.

To have some additional safety margin with respect to unexpected drop-outs and with respect to the use of a stratified analysis, it is therefore planned to enroll a total of 94 evaluable subjects into the study.

The abovementioned assumptions for the true proportions of response were thoroughly discussed and agreed with an advisory board, consisting of several experts in this field.

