The membership of each subject in the respective analysis populations will be determined before the statistical analysis in a data review meeting by a panel consisting of a medical expert from the sponsor, the clinical project manager, the data manager and the study statistician.

All protocol deviations documented during the conduct of the study or identified at the data review process prior to DB lock will be reviewed and classified as minor or major and with respect to their significance for the planned analyses. Only significant protocol deviations with the potential to affect the study results or to invalidate the interpretation of the data obtained will lead to exclusion of subjects from the PP sets. This classification of protocol deviations is the joint responsibility of the clinical study manager, the study statistician, and Octapharma's responsible medical expert, and will be performed and documented before the database is locked and the statistical analyses are performed.

8. General Issues for Statistical Analysis

The main analysis will be the comparison between Octagam 10% and placebo on basis of the efficacy measures assessed in the 16 week efficacy period.

To evaluate the sustained benefit of treatment with Octagam 10%, and also the safety and tolerability of Octagam 10% in subjects with DM, all data collected during treatment with Octagam 10% throughout the study period will be used.

In addition to the confirmatory evaluation of the primary endpoint, descriptive summaries will be presented for each of the primary and secondary target variables. In general, these summaries will be presented for all patients overall and by treatment group, for each of the 3 strata (GDA at screening mild|moderate|severe), as totals and by treatment group within each stratum.

Descriptive subgroup analyses will be performed with respect to age, sex, race, and region (U.S. vs. Non-U.S.).

Depending on the number of infusions with reduced dose of 1.0 g/kg in the extension period, measures and events associated with this dose regimen will be contrasted with the regular 2.0 g/kg dose scheme.

Continuous, quantitative variable summaries will in general include the number of subjects with non-missing values (N), mean, standard deviation, median, minimum and maximum, 1st and 3rd quartile.

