10.2. Secondary efficacy endpoints

All secondary efficacy endpoints will be analyzed and presented in full detail by means of descriptive statistics and inferential analyses as appropriate.

For TIS response at Week 16 by improvement category, the proportion of subjects with at least moderate improvement and the proportion of subjects with major improvement will be calculated together with subject counts and the associated 2-sided 95% confidence interval (CI) for the difference in the proportion of patients with improvement. Moreover, both treatment groups will be compared using a Cochran-Mantel Haenszel test, analogously as for the primary endpoint. The proportion of subjects in each treatment arm who meet confirmed deterioration criteria up to (including) Week 16 will be presented in the same way.

All mean changes to be evaluated as secondary endpoints (listed in section 3.2.2) will be presented by a full set of descriptive parameters: number of subjects with non-missing values, mean, standard deviation, median, minimum and maximum, 1st and 3rd quartile, 95% CI. Moreover, for all continuous secondary endpoints, an analysis of covariance (ANCOVA) will be used to analyze changes from baseline to Week 16. For patients who are switched to the alternate treatment before Week 16, the last value prior to switch will be carried forward to Week 16 and used to calculate change from baseline to Week 16. The model will include treatment and global disease activity as a fixed factor. Center will be included as random factor. The baseline value of the variable to be analyzed will be included as a covariate. Least square means will be derived and presented together with 95%-confidence intervals by treatment group. Moreover, two-sided 95% confidence intervals will be derived for the overall difference in least square means between Octagam and placebo treatment. As sensitivity analysis, a modified ANCOVA model will be used, where the changes from baseline to Week 16 are calculated based on Week 16 values, even if a patient is switched to the alternate

treatment before Week 16. To incorporate the switch into the model, the variable crossover (yes/no) which indicates if there was a switch to the alternate treatment will be included as additional factor into the ANCOVA model, as well as the treatment-by-cross-over interaction term.

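### The primary test is stratified by GDA but the only confidence interval specified for the primary effect is not, so the two can occasionally disagree

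*SAP*

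**What the plan says.** Randomisation uses three GDA strata (SAP 4.3: "The randomization scheme will be stratified according to the seriousness of disease before enrollment"). The primary comparison follows that design. Responder proportions are "compared by Cochran-Mantel-Haenszel test, stratified by global disease activity (randomization stratum), using two-sided alpha level of 0.05" (SAP 10.1), and SAP 6 gives the reason: "A stratified analysis using Cochran-Mantel-Haenszel test will finally be applied as primary analysis, to account for the stratification of the randomization". The trial "will be considered as success if the proportion of responders is significantly higher in the Octagam group", so the decision rests on the CMH test alone.

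The interval that accompanies the test is described differently: "an exact two-sided 95% confidence-interval will be constructed for the overall difference in the proportion of responders between Octagam and placebo group". It is to come from the exact risk-difference option of SAS PROC FREQ, with no strata or weights mentioned. Protocol 9.2.2 and the Study Outline say the same. The documents do not use the word unstratified; it is inferred from this wording.

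Two other items involve GDA. SAP 8 says "these summaries will be presented for all patients overall and by treatment group, for each of the 3 strata", which is descriptive. The logistic regression in SAP 10.1 includes GDA as a covariate but states no estimate or interval.

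SAP 10.2 pairs a CMH test with an "associated 2-sided 95% confidence interval (CI) for the difference in the proportion of patients with improvement" for at least moderate improvement and for major improvement, and presents confirmed deterioration in the same way. It names no interval method.

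**The concern.** A reader expects the interval beside a primary p-value to describe the same comparison. Here the test conditions on GDA stratum and the interval does not. If GDA predicts response, the stratified test removes between-stratum variation that the unstratified interval keeps, so a significant CMH result could be printed beside an interval that includes 0. That would happen in borderline results, where the interval is read most closely.

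Nothing else in the plan fills the gap. By-stratum summaries give no combined adjusted effect, and logistic regression is not on the risk-difference scale. The plan does match test and interval elsewhere: for continuous secondary endpoints, SAP 10.2 takes the interval for the difference from the same GDA-adjusted ANCOVA.

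What is at stake is coherent reporting of the primary result, not its validity.

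**Working it through.** **Inputs from the documents.** Response 0.6 vs 0.3, two-sided alpha 0.05, 80% power, Pearson chi-square, N = 84 (SAP 6); 94 planned, hence 47 per arm at 1:1 (SAP 4.3 and 6); early dropouts count as non-responders (SAP 10.1), so all 94 enter both test and interval.

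**Assumptions.** Strata of 12/23/12 or 9/24/14 per arm; response shifted between adjacent GDA strata by 0, ±0.1 or ±0.2; CMH without continuity correction. The SAP does not say which statistic orders the tables for the exact interval. Ordering by the plain difference is used unless stated.

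**1. The plan's own figure.** n per arm = [1.960·√(2·0.45·0.55) + 0.842·√(0.6·0.4 + 0.3·0.7)]² / 0.3² = 41.97, so 42 per arm and N = 84, as stated. Power at 47 per arm is 0.844.

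**2. One discordant table.** Strata 12/23/12 per arm; responders 9/11/3 on Octagam and 6/6/2 on placebo, that is 23/47 vs 14/47, difference 9/47 = 0.191. With m responders among N subjects in a stratum (N/2 per arm):

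- CMH numerator, Σ(x − m/2) = 1.5 + 2.5 + 0.5 = 4.5.
- CMH variance, Σ n₁n₀m(N − m)/[N²(N − 1)] = 1.467 + 2.739 + 1.033 = 5.239.
- z = 4.5/√5.239 = 1.966, p = 0.049.
- Ignoring strata, the numerator is still 4.5, but the variance is 47·47·37·57/(94²·93) = 5.669. Then z = 1.890, p = 0.059.

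| 95% interval | Lower | Upper |
|---|---|---|
| Planned exact, unstratified | -0.021 | 0.392 |
| Score (Miettinen-Nurminen), unstratified | -0.007 | 0.376 |
| Score, stratified, Mantel-Haenszel weights, N/(N − 1) | 0.001 | 0.372 |

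Only the stratified interval agrees with the test. Giving up exactness alone does not help.

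**3. How often.** Percentage of 200,000 simulated trials per scenario, at 60% vs 30% with strata balanced between arms, in which CMH is significant and the interval includes 0:

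| Shift between adjacent strata | Planned exact | Exact, score ordering | Unstratified score | Stratified score |
|---|---|---|---|---|
| 0 | 0.1 | 0.05-0.06 | 0.03-0.04 | 0 |
| ±0.1 | 0.3-0.4 | 0.3-0.4 | 0.2-0.3 | 0 |
| ±0.2 | 1.7-2.3 | 1.7-2.3 | 1.7-2.2 | 0 |

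The reverse conflict (planned interval excludes 0, CMH not significant) never occurred with balanced strata. It can occur with imbalance: at an assumed 14/23/10 vs 10/23/14 and a 0.2 shift, it arose in 4.3% of trials. With the imbalance the other way round, CMH was significant with 0 inside the interval in 12.0%.

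**4. Width is a separate matter.** At 28 vs 14 responders the planned interval is 0.087 to 0.489 (width 0.402) and the unstratified score interval 0.097 to 0.476 (0.379). The stratified score interval averages 0.379, 0.375 and 0.363-0.365 for shifts of 0, ±0.1 and ±0.2. The exact method therefore accounts for 0.402 − 0.379 = 0.023, and the strata for a further 0.000, 0.004 and 0.014-0.016.

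**5. Why the proposed interval matches.** At a difference of 0, the stratified score statistic with Mantel-Haenszel weights and the N/(N − 1) factor is the uncorrected CMH statistic. Without that factor the two disagreed in 0.2-0.9% of trials. A Mantel-Haenszel Wald-type interval excluded 0 with CMH non-significant in 0.3-2.5%.

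**6. SAP 10.2.** At assumed rarer rates, from 40 vs 20% down to 2 vs 10%, the stratified score interval covered 94.7-96.2% and agreed with CMH in every trial, although up to 47% of trials had a stratum with no events. If the exact option were carried over to SAP 10.2, which the SAP does not say, the choice of ordering would matter. With plain-difference ordering, CMH would be significant with 0 inside the interval in 7-8% (40 vs 20%), 20-22% (30 vs 10%) and 40-45% (20 vs 5%) of trials. With score ordering it would be 0.7-1.7%.

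**The case against.** The strongest reply is that nothing here is wrong. The success rule does not use the interval, the exact interval guarantees its coverage, and an overall difference is a legitimate thing to report. A 0.2 shift means response of 40/60/80% vs 10/30/50% across strata, and the documents support no gradient that steep; below it, conflict stays under half a percent. The SAP 10.2 percentages depend on a carry-over and an ordering that the SAP does not state. The remedy also has conditions: exact agreement needs the N/(N − 1) factor and CMH without continuity correction, and the SAP is silent on the correction. Finally, table specifications are deferred to a separate document, and Protocol 9.2.2 leaves further presentation detail to the SAP.

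Most of this stands and sets the weight of the point: conflict is rare, the larger rates are conditional, and no inference is invalid. It does not remove the mismatch. No section supplies a stratified risk difference with an interval, and one chosen after unblinding would be post hoc. The conditions on the remedy are a reason to write them into the text. The deferral to the SAP means the SAP wording is what matters most.

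**Conclusion.** The point holds, as an improvement to consider. The deciding test is stratified by GDA, and the only interval specified for the primary effect is not. At the planned rates with balanced strata they conflict in about 0.1% to 2.3% of trials, depending on how strongly GDA predicts response; marked imbalance between arms could raise this. Stratum sizes and GDA effects are assumptions, because the documents give neither. The success decision, type I error and power are unaffected, and the point estimate is unchanged when arms are balanced within strata. The extra width of the planned interval comes mostly from the exact method. Its conflict with CMH, once GDA is prognostic, comes mostly from omitting the strata. The missing interval method in SAP 10.2 is a separate, smaller gap.

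**What to change.** Before unblinding, put the following in SAP 10.1, with matching wording in Protocol 9.2.2 and the Study Outline:

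> The treatment effect will be reported as the Mantel-Haenszel-weighted risk difference stratified by GDA randomisation stratum, with a two-sided 95% stratified Miettinen-Nurminen score CI using Mantel-Haenszel weights and the N/(N − 1) variance factor, which agrees with the CMH test without continuity correction. The exact unstratified CI will be supportive.

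Also state which statistic orders the tables for the exact interval. In SAP 10.2, name the same stratified interval for at least moderate improvement, major improvement and confirmed deterioration.

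The cost is one sentence in each SAP section, the matching protocol text and one extra table line. The statistical price is that a score interval is asymptotic: simulated coverage at 60% vs 30% was 94.8-95.0%, against 96.1-97.1% for the exact interval, which is why the latter is kept. Narrowing relative to the unstratified score interval is not guaranteed either. With no GDA effect, about 65% of stratified intervals at 28 vs 14 responders were slightly wider than it (at most 0.383 against 0.379), though all stayed below the planned 0.402.

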10.2. Secondary efficacy endpoints

All secondary efficacy endpoints will be analyzed and presented in full detail by means of descriptive statistics and inferential analyses as appropriate.

For TIS response at Week 16 by improvement category, the proportion of subjects with at least moderate improvement and the proportion of subjects with major improvement will be calculated together with subject counts and the associated 2-sided 95% confidence interval (CI) for the difference in the proportion of patients with improvement. Moreover, both treatment groups will be compared using a Cochran-Mantel Haenszel test, analogously as for the primary endpoint. The proportion of subjects in each treatment arm who meet confirmed deterioration criteria up to (including) Week 16 will be presented in the same way.

All mean changes to be evaluated as secondary endpoints (listed in section 3.2.2) will be presented by a full set of descriptive parameters: number of subjects with non-missing values, mean, standard deviation, median, minimum and maximum, 1st and 3rd quartile, 95% CI. Moreover, for all continuous secondary endpoints, an analysis of covariance (ANCOVA) will be used to analyze changes from baseline to Week 16. For patients who are switched to the alternate treatment before Week 16, the last value prior to switch will be carried forward to Week 16 and used to calculate change from baseline to Week 16. The model will include treatment and global disease activity as a fixed factor. Center will be included as random factor. The baseline value of the variable to be analyzed will be included as a covariate. Least square means will be derived and presented together with 95%-confidence intervals by treatment group. Moreover, two-sided 95% confidence intervals will be derived for the overall difference in least square means between Octagam and placebo treatment. As sensitivity analysis, a modified ANCOVA model will be used, where the changes from baseline to Week 16 are calculated based on Week 16 values, even if a patient is switched to the alternate

treatment before Week 16. To incorporate the switch into the model, the variable crossover (yes/no) which indicates if there was a switch to the alternate treatment will be included as additional factor into the ANCOVA model, as well as the treatment-by-cross-over interaction term.

In case the proportion of patients with missing values is greater than 10%, or if the modified ANCOVA detailed above gives a signal of divergence, the concerned data will be further reviewed and analyzed.

The time to at least minimal, at least moderate and major improvement in TIS, and the time to confirmed deterioration in the First Period and overall, will be summarized using based on Kaplan-Meier estimates that will also be presented graphically. For the analysis of improvement variables in the first period, the time to event will be censored at the time of switch to the alternate treatment group. A stratified log-rank test will be applied for time to event variables to compare both treatment groups. Cox regression models may be applied additionally to include randomization stratum and further baseline covariates in the analysis.

To also include all data from the extension period in such Kaplan-Meier analyses, we will look at the abovementioned events and their timely relationship to the first infusion of Octagam.

To confirm the sustained benefit of treatment with Octagam 10% , response rates at Week 40 and changes from baseline to Week 40 will be presented descriptively (overall and by randomized treatment), including 95% confidence intervals.

All individual core set measures (CSMs) used for the TIS, and all other efficacy endpoints will be analyzed and presented in full detail by means of descriptive statistics, including summary and frequency tables, as well as graphs according to the general principles described in sections 8 and 12.

The development of each CSM over time will be presented graphically.

The detailed list of all tables, figures and graphs, and the analysis populations used for each analysis will be provided in a separate document later, when all feedback from authorities will be available.

11. Safety and Tolerability Analyses

The safety analysis will comprise descriptive statistics, tabulations and listings of all treatment emergent adverse events (TEAEs), safety laboratory results, viral markers, vital signs, Wells' scores, Doppler scan results, and physical examination findings.

